7 STATISTICAL ANALYSES

7.1 General Methods

The stratification variables included in all the statistical models will be based on the IWRS stratification data used for the stratification of the randomization, while the subgroups used for the analyses (e.g., subgroup of subjects with stimulated whole salivary flow of at least 0.1mL/min at both screening and baseline) will be defined based on data entered on the CRF.

7.1.1 Change from Baseline

Change from baseline to any Visit t in Double-Blind Treatment Period is defined as follows:

$$C_{\text{Visit } t} = M_{\text{Visit } t} - M_{\text{baseline}}$$

where:

- $C_{\text{Visit } t}$ is the change from baseline at Visit t ,
- $M_{\text{Visit } t}$ is the measurement at Visit t ,
- M_{baseline} is the measurement at baseline.

The “Visit t ” and baseline to which a measurement belongs is determined using the conventions described in [Section 8.1](#)

7.1.2 Percent Change from Baseline

Percent change from baseline to any Visit t in Double-Blind Treatment Period is defined as follows:

$$P_{\text{Visit } t} = 100 \times (M_{\text{Visit } t} - M_{\text{baseline}}) / M_{\text{baseline}}$$

where:

- $P_{\text{Visit } t}$ is the percent change from baseline at Visit t ,
- $M_{\text{Visit } t}$ is the measurement at Visit t ,
- M_{baseline} is the measurement at baseline.

The “Visit t” and baseline to which a measurement belongs is determined using the conventions described in [Section 8.1](#).

7.1.3 Longitudinal Repeated Measures Analysis

Primary Endpoint (ESSDAI)

Changes from baseline over time for the primary endpoint, ESSDAI, will be analyzed using a longitudinal repeated measures analysis. The model will include the fixed categorical effects of treatment, day (is a windowed time point), Baseline oral corticosteroid use (yes/no), baseline hydroxychloroquine use (yes/no), baseline stimulated salivary flow ($< 0.1\text{mL}/\text{min}$, $\geq 0.1\text{mL}/\text{min}$), Japan (yes/no), treatment-by-day interaction, baseline oral corticosteroid use-by-day interaction, baseline hydroxychloroquine use-by-day interaction, baseline stimulated salivary flow-by-day interaction, Japan-by-day interaction as well as, the continuous fixed covariate of baseline ESSDAI and baseline ESSDAI -by-day interaction. An unstructured covariance matrix will be used to represent the correlation of the repeated measures within each subject. The parameter estimations will be based on the assumption of data being missing at random (MAR) and using the method of restrictive maximum likelihood (REML). The degrees of freedom will be calculated using the Kenward-Rogers method. Adjusted mean changes (LSMeans) with corresponding SE and 95% CI per treatment arm will be provided. The difference in adjusted means (LSMEANS) between abatacept and placebo at the primary time point, Day 169, and corresponding 95% CI and p-value based on this longitudinal repeated measures model will be provided. The analysis is using the modified ITT analysis population and all efficacy measurements collected up to last dose in Double-Blind Period + 42 days (and prior to start of open-label treatment).

In case of non-convergence of the preferred longitudinal model, memory space issues, or other computational issues the following back-up models are defined and will be applied sequentially.

The first back-up model that resolves the computational issues will be used.

- In the first backup model, the repeated statement will specify a spatial power covariance matrix instead of the unstructured variance-covariance matrix; and intercept and slope will be specified as random effects on a subject level. All terms and interactions will be as for the primary model.
- In the second backup model, in addition to specifying a spatial power covariance matrix, the model will not include terms for the interactions between the stratification variables (baseline oral corticosteroid use, baseline hydroxychloroquine use, baseline stimulated salivary flow, Japan) and day. This means that the model will include the following terms: the fixed categorical effects of treatment, day (is a windowed time point), baseline oral corticosteroid use, baseline hydroxychloroquine use, baseline stimulated salivary flow, Japan, treatment-by-day interaction, and the continuous fixed covariate of baseline ESSDAI score and baseline ESSDAI score -by-day interaction.
- In the third backup model, the spatial power covariance structure will be used and the model will not include any terms for interactions between baseline variables and day. Therefore the model will include the following terms: the fixed categorical effects of treatment, day (is a windowed time point), baseline oral corticosteroid use, baseline hydroxychloroquine use,

baseline stimulated salivary flow, Japan, treatment-by-day interaction, and the continuous fixed covariate of baseline ESSDAI score.

Patterns of missing data from Day 1 up to Day 169 will be provided:

- Patterns of missing data for the primary endpoint of change from baseline in ESSDAI over time will be displayed separately for the two treatment groups up to Day 169. Data collected more than 42 days after the subject discontinued from the study will not be considered as missing for this summary.
- In addition, patterns of missing data including data collected more than 42 days after a subject discontinued study treatment up to Day 169 will be provided.

All patterns (patterns of monotone missing and non-monotone missing) observed will be summarized for each treatment group separately.

Key Secondary Endpoints (ESSPRI and Stimulated Salivary Flow)

Changes from baseline over time for the key secondary endpoint, ESSPRI, will be analyzed using a longitudinal repeated measures analysis. The model will include the fixed categorical effects of treatment, day (is a windowed time point), Baseline oral corticosteroid use (yes/no), baseline hydroxychloroquine use (yes/no), baseline stimulated salivary flow ($< 0.1\text{mL}/\text{min}$, $\geq 0.1\text{mL}/\text{min}$), Japan (yes/no) treatment-by-day interaction, baseline oral corticosteroid use-by-day interaction, baseline hydroxychloroquine use-by-day interaction, baseline stimulated salivary flow-by-day interaction, Japan-by-day interaction as well as, the continuous fixed covariate of baseline ESSPRI and baseline ESSPRI -by-day interaction. An unstructured covariance matrix will be used to represent the correlation of the repeated measures within each subject. The parameter estimations will be based on the assumption of data being missing at random (MAR) and using the method of restrictive maximum likelihood (REML). The degrees of freedom will be calculated using the Kenward-Rogers Method. Adjusted mean changes (LSMeans) with corresponding SE and 95% CI per treatment arm will be provided. The difference in adjusted means (LSMEANS) between abatacept and placebo at the primary time point, Day 169, and corresponding 95% CI and p-value based on the longitudinal repeated measures above will be provided. The analysis is using the modified ITT analysis population and all efficacy measurements collected up to last dose in Double-Blind Period + 42 days (and prior to open-label treatment).

In case of computational or non-convergence issues of the model, the following back-up models will sequentially be applied and the first back-up model that resolves the issues will be used. First a spatial power covariance matrix will be used instead of an unstructured covariance. The second back-up model will use a spatial covariance matrix and remove the interactions with baseline stratification from the model. The third back up model will include the spatial power covariance matrix and remove all interactions between baseline and day from the model.

Changes from baseline over time for the key secondary endpoint, stimulated salivary flow, will be analyzed using a longitudinal repeated measures analysis. This analysis will be provided for the subgroup of subjects with stimulated whole salivary flow of at least $0.1\text{mL}/\text{min}$ at both screening

and baseline. The model will include the fixed categorical effects of treatment, day (is a windowed time point), Baseline oral corticosteroid use (yes/no), baseline hydroxychloroquine use (yes/no), Japan (yes/no), treatment-by-day interaction, baseline oral corticosteroid use-by-day interaction, baseline hydroxychloroquine use-by-day interaction, Japan-by-day interaction as well as, the continuous fixed covariate of baseline stimulated salivary flow and baseline stimulated salivary flow-by-day interaction. An unstructured covariance matrix will be used to represent the correlation of the repeated measures within each subject. The parameter estimations will be based on the assumption of data being missing at random (MAR) and using the method of restrictive maximum likelihood (REML). The degrees of freedom will be calculated using the Kenward-Rogers Method. Adjusted mean changes (LSMeans) with corresponding SE and 95% CI per treatment arm will be provided. The difference in adjusted means (LSMEANS) between abatacept and placebo at the primary time point, Day 169, and corresponding 95% CI and p-value based on the longitudinal repeated measures above will be provided. The analysis is using the modified ITT analysis population and all efficacy measurements collected up to last dose in Double-Blind Period + 42 days (and prior to open-label treatment).

In case of computational or non-convergence issues of the model, the following back-up models will sequentially be applied and the first back-up model that resolves the issues will be used. First, a spatial power covariance matrix will be used instead of an unstructured covariance. The second back-up model will use a spatial covariance matrix and remove the interactions with baseline stratification from the model. The third back-up model will include the spatial power covariance matrix and remove all interactions between baseline and day from the model.

Patterns of missing data for the change from baseline over time for the key secondary endpoints will be assessed using the same methods that were described for the primary endpoint in the previous section.

7.1.4 Binary Secondary Endpoints

The binary secondary efficacy endpoints, e.g., the proportion of subjects with a decrease in ESSDAI of at least 3 from baseline to Day 169 and the proportion of subjects with a decrease in the ESSPRI of at least 1 to Day 169, will be analyzed with a logistic regression including treatment, oral corticosteroid use, hydroxychloroquine use, stimulated salivary flow, Japan and baseline value in the model. The odds ratio along with its 95% confidence interval will be provided. The construction of CIs for differences in response rates between treatment groups will be based on minimum risk weights to account for randomization stratification factors, unless otherwise noted.

In case there are fitting issues with the minimum risk weights model including the 4 randomization stratification variables (too small strata), the first back-up model will exclude the Japan and stimulated salivary flow randomization stratification factors. The second back-up model will exclude all randomization stratification factors. The 95% CI within each treatment arm will be based on normal approximation.

A missing responder value at Day 169 due to discontinuation or for other reasons will be imputed as a non-responder. No p-values will be provided for the binary secondary efficacy endpoints

except for the proportion of subjects with a decrease in ESSDAI of at least 5 from baseline to Day 169 and the proportion of subjects with a decrease in the ESSPRI of at least 1 to Day 169.

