3.3.1 Inclusion Criteria

1. Signed Written Informed Consent

- a. Subject is willing to participate and has signed informed consent.

2. Target Population

- a. Subjects must meet the proposed 2015 ACR/EULAR Classification Criteria for SS (Sjögren’s Syndrome) ([Appendix 3](#)), as specified for pSS (primary Sjögren’s Syndrome).

- i. If a prior labial salivary or parotid gland biopsy was performed, information will be reported in the CRF and the report should be obtained for the source documents.
- b. Subjects should have pSS that is refractory to symptomatic or local therapy (eg, NSAIDs).
- c. ESSDAI \geq 5 at screening.
- d. Positive anti-SSA/Ro at screening.
- e. Stimulated salivary flow of at least 0.1 mL/min at screening and randomization in at least 124 subjects (72%). Enrollment of subjects with less than 0.1 mL/min of stimulated salivary flow at screening and/or randomization may be closed after 48 of such subjects are randomized.
- f. Subject Re-enrollment: This study permits the re-enrollment of a subject that has discontinued the study as a pre-treatment failure (ie, a “screen failure”, the subject has not been randomized / has not been treated). If re-enrolled, the subject must be re-consented and will receive a new PID.

3. Age and Reproductive Status

- a. Males and Females, ages \geq 18 (or age of majority).
- b. Women of childbearing potential (WOCBP) must have a negative serum or urine pregnancy test (minimum sensitivity 25 IU/L or equivalent units of HCG) within 24 hours prior to the start of study drug.
- c. Women must not be breastfeeding.
- d. Women of childbearing potential (WOCBP) must agree to follow instructions for method(s) of contraception for the duration of treatment with study drug(s) (abatacept/placebo) plus 5 half-lives of study drug (70 days) plus 30 days (duration of ovulatory cycle) for a total of 100 days post-treatment completion.
- e. Males who are sexually active with WOCBP must agree to follow instructions for method(s) of contraception for the duration of treatment with study drug(s) (abatacept/placebo) plus 5 half-lives of the study drug (70 days) plus 90 days (duration of sperm turnover) for a total of 160 days post-treatment completion. In addition, male subjects must be willing to refrain from sperm donation during this time.

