7.5.2.2 Categorical Endpoints

The binary secondary endpoints defined in this study are:

- Proportion of subjects who achieve a minimally clinically important improvement (of at least 3 points) in the ESSDAI at all measured time points up to Day 169 in the full population, among those with stimulated whole salivary flow of at least 0.1mL/min at both screening and

Double-blind analysis over time

The binary endpoints given above at each timepoint (at which endpoint is collected) up to Day 169 will be analyzed as specified in Section 7.1.4. The modified ITT population will be used. Missing values will be imputed as non-responders. In addition, the secondary binary efficacy endpoints will also be analyzed for 2 subgroups:

- subgroup of subjects with stimulated whole salivary flow of at least 0.1mL/min at both screening and baseline
- subgroup of subjects with stimulated whole salivary flow of less than 0.1mL/min at screening or baseline.

The subgroup analyses mentioned in the 2 bullets above will only be provided if there are at least 10 subjects in each treatment group in each of the subgroups.

The logistic model for these subgroup analysis will not include the stimulated salivary flow stratification variable.

The response rate (%) and 95% CI over time will be plotted for each treatment group up to Day 169 for the secondary binary endpoints.

Analysis from Day 1 up to Day 365

The binary endpoints given above at each timepoint in double-blind and open-label period up to Day 365 will be summarized by a point estimate for the response rate and corresponding 95 % CI for the 2 original randomized treatment arms. No treatment differences will be provided for any timepoints during the open-label period.

The modified ITT population will be used. Missing values will be imputed as non-responders. In addition, the secondary binary efficacy endpoints will also be analyzed for 2 subgroups:

- subgroup of subjects with stimulated whole salivary flow of at least 0.1mL/min at both screening and baseline
- subgroup of subjects with stimulated whole salivary flow of less than 0.1mL/min at screening or baseline.

The subgroup analyses mentioned in the 2 bullets above will only be provided if there are at least 10 subjects in each treatment group in each of the subgroups.

The response rate (%) and 95% CI over time will be plotted for each treatment group during the double-blind and open-label periods up to Day 365 for the secondary binary endpoints.

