7.5.2.3 Subgroup Analyses

All analyses described in this section will be performed on the modified ITT Analysis Population. All subgroups will be defined based on the data as entered on the CRF; no IWRS will be used for any subgroup analysis.

Table 7.5.2.3-1 shows the subgroups of interest for analyses of the primary efficacy endpoint of Change from Baseline at Day 169 (ESSDAI). The analysis will be using the methods described in Section 7.1.3 for each level of each subgroup, except that all stratification variables and the baseline ESSDAI day-by-day interaction will be removed from the model for this subgroup analysis. If the value of the grouping variable cannot be determined for a subject, the subject will be excluded from the corresponding subgroup analysis. Only subgroups with at least 10 patients in both treatment arms will be considered.

A forest plot showing per subgroup the estimates per treatment group and the treatment differences will be provided. The sample size for each treatment group in the subgroup will be presented along with the adjusted mean change from baseline (with 95% CI) and the treatment difference (with 95% CI).

Table 7.5.2.3-1: Subgroups of Interest

Subgroup factor	Categories
Age	< 65 Years Old
	≥ 65 Years Old
Baseline Weight	< 60kg
	60 - 100kg
	> 100kg
Gender	Male
	Female
Race	White
	Black
	Asian
	Other
Geographic Region	North America
	South America
	Asia
	Europe
	ROW
	Baseline Hydroxychloroquine use as recorded in CRF
	No
Baseline oral corticosteroid use as recorded in CRF	Yes
	No
Baseline Stimulated Salivary Flow as recorded in CRF	< 0.1mL/min
	≥ 0.1mL/min

Table 7.5.2.3-1: Subgroups of Interest

Subgroup factor	Categories
Japan as recorded in CRF	Yes
	No
ESSDAI categories at Day 1	Low < 5
	Moderate $5 \leq \text{ESSDAI} \leq 13$
	High ≥ 14

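### In the low-flow subgroup, the responder odds ratios come from an ordinary five-predictor logistic model in about 48 or fewer subjects, with no fallback if the fit separates

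*SAP*

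**What the plan says.** SAP 7.1.4 states that each responder endpoint "will be analyzed with a logistic regression including treatment, oral corticosteroid use, hydroxychloroquine use, stimulated salivary flow, Japan and baseline value in the model". It adds: "The odds ratio along with its 95% confidence interval will be provided". No penalised or exact method is named. A missing response counts as non-response.

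SAP 7.5.2.2 applies this at every double-blind visit and in both salivary-flow subgroups. It makes one change there: "The logistic model for these subgroup analysis will not include the stimulated salivary flow stratification variable". Five predictors remain: treatment, oral corticosteroid use, hydroxychloroquine use, Japan and baseline value. The subgroup analyses "will only be provided if there are at least 10 subjects in each treatment group in each of the subgroups".

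The only fallback in 7.1.4 concerns a different quantity, the confidence interval for the difference in response rates. It opens with "In case there are fitting issues with the minimum risk weights model including the 4 randomization stratification variables", then drops Japan and flow, and then all strata.

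Protocol 3.3.1 plans at least 124 subjects with flow of 0.1 mL/min or more. It allows low-flow enrolment to close after 48 and sets no minimum for that group.

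**The concern.** A maximum-likelihood logistic fit with six parameters in 20 to 48 subjects can separate: some combination of predictors splits responders from non-responders, and at least one coefficient has no finite estimate. Fits that do not separate tend to push a real odds ratio further from 1.

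Protocol 8.3.2 lists three responder endpoints (ESSDAI by 3 points, ESSDAI by 5 points, ESSPRI by 1 point). Six post-baseline double-blind visits give 3 x 6 = 18 such fits in the low-flow subgroup. If one fails, the SAP gives no rule, and the analyst must choose a model after unblinding.

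Elsewhere the SAP does anticipate this kind of trouble. It gives fallbacks for the repeated-measures models, the risk-weighted difference and the multiple imputation. The ESSDAI subgroup models in 7.5.2.3 follow the primary model "except that all stratification variables and the baseline ESSDAI day-by-day interaction will be removed from the model".

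**Working it through.** **The plan's own figures.** The documents give no power or precision for the responder endpoints. Their stated powers reproduce with an exact two-sided t-test: ESSDAI (86 per arm, difference 3, SD 4.8) 98.3%; ESSPRI (86 per arm, difference 1, SD 2) 90.3%; salivary flow (62 per arm, 0.165, SD 0.275) 91.2%. The product 0.98 x 0.90 x 0.91 = 80.3% also agrees.

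**Subgroup sizes.** 124/172 = 72%. The remainder is 172 - 124 = 48, or 24 per arm. The permitted floor is 10 per arm, 20 in total. The higher-flow subgroup is planned at 124/2 = 62 per arm or more.

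**Model checked.** logit P(response) = intercept + treatment + corticosteroid + hydroxychloroquine + Japan + baseline value, which has six parameters.

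**Assumptions not in the documents.** Corticosteroid use 30%, hydroxychloroquine use 50%, Japan 15% (varied from 5% to 30%); placebo response 20%, 35% or 50%; true odds ratio 1 or 2.5; covariate log odds ratios 0.3; baseline log odds ratio 0.4 per SD.

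**Method.** There were 1,000 simulated data sets per setting (400 at 62 per arm). Separation was detected by linear programming. The treatment coefficient was counted as diverging if the outcome was constant, or if the fit separated and the log odds ratio passed 8 in absolute value. Firth's penalised likelihood was the comparator.

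Results with Japan at 15%. The first two result columns span both true odds ratios; the last two are geometric means when the true odds ratio is 2.5:

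| Per arm | Any coefficient separates | Treatment OR diverges | ML, non-separated fits | Firth |
|---|---|---|---|---|
| 10 | 44-75% | 6-33% | 3.5-4.1 | 2.6-2.8 |
| 15 | 21-50% | 0.1-11% | 3.2-3.8 | 2.5-2.7 |
| 24 | 5-23% | 0-1.4% | 2.9-3.0 | 2.5-2.6 |
| 62 | 0-0.7% | 0% | 2.6-2.9 | 2.5-2.7 |

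**Sensitivity to Japan** (placebo response 35%, odds ratio 2.5). Moving from 30% to 5% Japanese subjects takes separation from 0.2% to 42% at 24 per arm, and from 28% to 58% at 10 per arm. At 10 per arm with Japan at 30% the ML average is 3.1, so the range there is 3.1-4.1. Those averages are unstable because so many fits drop out.

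**Size of the overstatement.** At 24 per arm, 2.88/2.5 = 1.15 and 3.04/2.5 = 1.22, so 15-22%. At 10 per arm, 3.07/2.5 = 1.23 and 4.15/2.5 = 1.66, so 23-66%.

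**No true effect.** The ML geometric mean is 0.90-1.04 at every size. At 10 per arm, 28-30% of non-separated fits still give an odds ratio above 2, which is imprecision and not bias.

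**The case against.** A reader might infer that responder odds ratios in both flow subgroups will often be infinite or inflated. The documents do not support that, for these reasons:

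- **Scope.** The higher-flow subgroup is planned at 62 per arm or more, where separation is at most 0.7%.
- **Floor against plan.** Ten per arm is a reporting threshold. About 24 per arm is the planning figure.
- **What separates.** At 24 per arm it is mostly a nuisance term such as Japan, and the treatment odds ratio usually stays finite.
- **Bias.** Overstatement needs a true effect. The model does not manufacture benefit where there is none.
- **Consequence.** These endpoints are outside the hierarchy in SAP 7.5. Differences in response rates, with their own back-up models, and plotted response rates are reported as well, so a failed fit still leaves the subgroup described.
- **The comparison with 7.5.2.3.** The direct counterpart is 7.5.2.1, where the continuous flow-subgroup models also drop only the flow factor. The logistic model is consistent with that.
- **A simpler cure.** Ordinary ML with treatment and baseline value only removes most of the problem. With a true odds ratio of 2 and 24 per arm, separation falls to 0% at 30-50% response and the average is about 2.1. At 10 per arm it falls from about 51-52% to 2-3%. At 10% response, however, it is still 8% and 42% respectively.

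All of this stands as a limit on size. It does not supply the missing rule for a logistic fit that fails, and it does not make ordinary ML the better estimator in the low-flow subgroup.

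**Conclusion.** The point holds for the low-flow subgroup only. The plan commits to an estimator that does worse there than a readily available alternative, and it says nothing about a failed fit.

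At the planned size the effect is moderate: occasional to fairly frequent separation, rarely in the treatment term, and a real odds ratio overstated by roughly a fifth. It becomes serious only if the subgroup falls well towards 10 per arm.

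The missing fallback is certain from the text. The percentages are not: they rest on assumed prevalences and response rates, and at 24 per arm the share of Japanese subjects alone moves separation from 0.2% to 42%. Response below 20%, which is possible at early visits, would raise the rates further. The primary and key secondary conclusions are unaffected.

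**What to change.** In SAP 7.1.4 and 7.5.2.2, state that the low-flow subgroup logistic models are fitted with Firth's penalised likelihood and profile-likelihood 95% intervals. Name the same method as the fallback for separation or non-convergence of any other logistic fit.

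Reducing the subgroup model to treatment and baseline value, in line with the removal of strata in 7.5.2.3, is optional. It would give up adjustment for the remaining randomisation factors.

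The cost is a few words of SAP text and one program option (FIRTH). The downside is slight shrinkage of the odds ratios.

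### Within-arm response-rate intervals rest on the normal approximation, which covers below 95% and can give negative or zero-width limits in the small salivary-flow subgroup

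*SAP*

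**What the plan says.** SAP 7.1.4 sets the method for the binary secondary endpoints: a logistic model for the odds ratio, minimum-risk weights for the difference in response rates and, for each arm on its own, "The 95% CI within each treatment arm will be based on normal approximation". It names no small-sample alternative for that last interval. Its back-up rules open with "In case there are fitting issues with the minimum risk weights model including the 4 randomization stratification variables" and concern the difference between arms, not the within-arm interval.

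SAP 7.5.2.2 carries this forward: the binary endpoints at each time point "up to Day 169 will be analyzed as specified in Section 7.1.4". The analysis is repeated for subjects with stimulated flow of at least 0.1 mL/min at both screening and baseline, and for those below 0.1 mL/min at either. The condition is that these analyses "will only be provided if there are at least 10 subjects in each treatment group in each of the subgroups". The results are also shown graphically: "The response rate (%) and 95% CI over time will be plotted for each treatment group up to Day 169". On missing data, "Missing values will be imputed as non-responders".

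A later paragraph of 7.5.2.2 asks for response rates with 95% intervals by original arm up to Day 365. It neither names a method nor cites 7.1.4.

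**The concern.** The Wald interval is centred on the observed proportion and takes its width from it. With few subjects or few responders, both are poor guides. Coverage then falls below 95%, the lower limit can be negative, and with no responders the interval shrinks to the single point 0%.

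These conditions are most likely in the low-flow subgroup, which is small by design, and for the stricter responder definitions. Non-responder imputation lowers the observed rates further. At stake is whether the plotted error bars can be read as 95% intervals where the data are sparsest.

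**Working it through.** **Plan's own figure.** The only figure is the nominal 95%. No expected response rate is stated.

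**Sizes.**
- 10 per arm: reporting floor, SAP 7.5.2.2.
- About 24 per arm: Protocol 3.3.1 lets low-flow enrolment close after 48 subjects; 48 / 2 = 24 at 1:1.
- 86 per arm: full population, SAP 5.

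**Response rates (assumed).** A rough anchor uses the planning SDs in SAP 5, with normally distributed changes and no mean improvement in the arm. Rate = Φ(−threshold / SD):
- ESSDAI decrease of at least 3, SD 4.8: Φ(−0.625) = 27%
- ESSDAI decrease of at least 5, SD 4.8: Φ(−1.042) = 15%
- ESSPRI decrease of at least 1, SD 2: Φ(−0.5) = 31%

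Over the SAP's ESSDAI SD range of 3.6 to 6.3, these become 20–32% for a decrease of at least 3 and 8–21% for at least 5. Mean improvement raises the rates; non-responder imputation lowers them. Rates of 5%, 10% and 20% are added to show the range.

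**Formulas.** With x responders out of n and p̂ = x/n:
- Wald: p̂ ± 1.96 √(p̂(1 − p̂)/n)
- Exact coverage at true rate p: the sum of binomial probabilities P(X = x) over every x whose interval contains p.

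For n = 24 and p = 10%, the intervals containing 10% are those for x = 1 to 6, and P(1 ≤ X ≤ 6) = 91.3%. For p = 20% they are x = 3 to 9, and P(3 ≤ X ≤ 9) = 87.3%.

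| True rate | Wald, n=10 | Wilson, n=10 | Wald, n=24 | Wilson, n=24 | Wald, n=86 |
|---|---|---|---|---|---|
| 5% | 40% | 91% | 71% | 97% | 93% |
| 10% | 65% | 93% | 91% | 97% | 93% |
| 15% | 79% | 95% | 89% | 96% | 94% |
| 20% | 89% | 97% | 87% | 96% | 93% |
| 27% | 93% | 97% | 91% | 94% | 94% |
| 31% | 85% | 92% | 95% | 95% | 93% |

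Coverage moves up and down with the rate because the data are discrete, so single entries should not be over-read.

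**Negative lower limits.** The Wald lower limit is below zero when 0 < x < 3.84n/(n + 3.84). At n = 24 the bound is 3.31, so x = 1, 2 or 3. P(1 ≤ X ≤ 3) is 71% at a true rate of 10% and 26% at 20%.

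**Zero width (no responders).** The probability is (1 − p)^n. At n = 24: 0.90^24 = 8.0% and 0.85^24 = 2.0%. At n = 10: 0.90^10 = 35%.

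**Examples.** With 0/10, Wald gives 0% to 0% and Wilson 0% to 27.8%. With 1/10, Wald gives −8.6% to 28.6% and Wilson 1.8% to 40.4%.

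**The case against.** The strongest case against is that this matters little, and most of that stands. The intervals describe one arm at a time. Arms are compared through the odds ratio and the minimum-risk-weight difference. The binary endpoints are outside the hierarchy in SAP 7.5, and only two carry nominal p-values. Type I error, the primary analysis and the key secondary analyses are untouched.

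Several stronger readings are tempting and are not supported:

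- **Coverage collapses to 40–65%.** This needs both 10 per arm and true rates of 5–10% (or 90–95%). Ten is a reporting floor, not a planned size, and the documents give no such rates. On the rough anchor above, only the decrease of at least 5 in ESSDAI, near the smallest SD, falls in that range. On the other side, 48 is the point at which low-flow enrolment may close, and nothing requires it to be reached, so arms below 24 are possible.
- **The intervals are simply too narrow.** At 1/10 the widths are 37.2 points (Wald) and 38.6 (Wilson). The fault there is mainly location.
- **The SAP prescribes this method to Day 365.** That is an inference. The Day 365 paragraph names no method, and parts of 7.5.2.2 are missing from the public text.
- **The same fault extends to the logistic model in these subgroups.** How that model is handled when data are sparse is a separate matter, and this point does not rest on it.

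The wording could also mean a continuity-corrected interval. That would remove the zero-width case and give about 100% coverage at n = 10 and a 5% rate. At a 10% rate, coverage would still be 65%. The uncorrected form is the usual reading, but it is an assumption.

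**Conclusion.** The point holds as a minor one. At about 24 per arm, coverage is 87–95% for true rates of 10–31% and 71% at 5%, against 94–97% for Wilson. Negative lower limits would be common at rates of 10–20%, and zero-width intervals occasional (8% at a 10% rate, 2% at 15%). At the 10-per-arm floor, coverage is 79–93% for rates of 15–31%. At 86 per arm it is 93–94% at the tabulated rates, so the full-population intervals are close to nominal.

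This rests on three assumptions: the uncorrected Wald interval, response rates that the documents do not state, and a low-flow subgroup of about 48 split evenly. No confirmatory conclusion is affected. What is affected is the reading of the responder tables and plots in the low-flow subgroup.

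**What to change.** In SAP 7.1.4, replace the normal-approximation within-arm interval with the Wilson score interval for all visits and subgroups. In SAP 7.5.2.2, state that the same method applies to the summaries and plots up to Day 365, which at present name none.

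The cost is one sentence in 7.1.4, a cross-reference in 7.5.2.2 and a standard software option. No new data are needed. The full-population intervals would change little. The Wilson interval stays within 0–100% and does not collapse when there are no responders.
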